10.2 Primary Analysis of Primary Efficacy Endpoint

The primary efficacy endpoint is the change from baseline to Week 96 visit on the CDR--SB score. The primary analysis population will be subjects in the ITT dataset and the primary analysis will be a likelihood-based, mixed-effects model, repeated measures (MMRM) analysis of the change from baseline to each post-baseline assessment up to and including Week 96. The model will include fixed, categorical effects for treatment, site, visit, baseline score-by-visit and treatment-by-visit interactions, with continuous fixed covariate for baseline score. The primary comparison will be the contrast between each ABBV-8E12 dose group and placebo group at Week 96. Contrasts between each ABBV-8E12 dose group and placebo at Weeks 24, 48, 72, and overall across the treatment period will be obtained and will be considered as secondary. An unstructured (co)variance structure will be used to model the within-patient errors. The same (co)variance structure will also be used for all MMRM analyses for secondary efficacy variables. Satterthwaite's approximation will be used to estimate denominator degrees of freedom.

The following statistics will be presented on the statistical table of MMRM analysis for change from baseline to each visit (Weeks 24, 48, 72, and 96): descriptive statistics

(number of non-missing observations, mean, standard deviation, minimum and maximum) for each treatment group. Within group LS mean and standard error will be presented for each treatment group. LS mean, standard error, 95% confidence interval and two-sided *P* values for comparisons between each ABBV-8E12 dose group and placebo at each post-baseline visit will also be presented. The LS mean, standard error, 95% confidence interval and two-sided *P* values of treatment difference comparing each ABBV-8E12 dose group with placebo across the treatment period will be included in the output as well.

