An analysis will be performed for plasma total tau concentration and for plasma NFL concentration. If the data are reported for other plasma concentration variables, an analysis like that described for plasma total tau concentration will be performed, provided that the proportion of measurements that are outside the limits of quantification and the magnitude of the lower limit do not make the methodology inappropriate.

A MMRM analysis will be performed on the data from scheduled times of measurement. The model will include the baseline value as a covariate, have classification of subjects by treatment, an effect for time (classification) and will include an effect for the interaction of treatment and time of measurement. The initial model will also allow the regression coefficient for the baseline value to vary with time (an effect for interaction of time and the baseline value), but this feature will be removed from the model if the statistic on this interaction is not significant at level 0.100. The subjects of each treatment group will be viewed as a random sample, and an appropriate structure for the covariance matrix of the measurements of a subject will be selected. Within the framework of this model, the mean across the scheduled times of measurement will be estimated for each treatment. Also, tests on differences of effect among the dose levels (with placebo considered a dose level) will be performed within the framework of the model. Tests on the dose level main effects will be performed as described for dose level effects in the analysis of covariance for CSF free tau concentration and CSF total tau concentration. These same tests will be provided for each time of measurement in the framework of the MMRM model, and the tests for the individual times will be given the greater attention if the statistic on the interaction of treatment and time of measurement is significant at level 0.100.

Analysis of Volumetric MRI Variables

For volumetric MRI variables, descriptive statistics will be provided for the baseline value, for each scheduled time after that and for the changes from baseline. An MMRM analysis will be performed like that described for plasma NFL concentration, but with an additional covariate, estimated total intracranial volume (eTIV), in the model. The

regression coefficient for eTIV will not vary with time, as may be allowed for the vMRI baseline value.

Analysis of Tau PET Scan Variables

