For each region of the brain for which SUVR values are obtained, a joint analysis will be performed for the two scheduled times of evaluation during treatment (Week 44 and Week 96). The analysis will be like that described for plasma NFL concentration with some additional assumptions made. The model will be that of a MMRM analysis even though there are only two times of measurement. The baseline value will be a covariate, with the regression coefficient assumed to be the same for the two times of measurement. Compound symmetry will be assumed for the covariance matrix of the error terms of the two times of measurement. If data are reported for other continuous variables that reflect the extent of tau pathology, a similar approach will be used for their analysis.

Consideration of Premature Discontinuations

The possibility of bias from missing data of subjects who prematurely discontinue for reasons possibly related to study drug will be addressed. If it is concluded that there may be a bias of meaningful magnitude as a result of premature discontinuation, sensitivity analyses may be carried out. Also, some imputation of missing values for subjects who prematurely discontinue might be done.

Relationship with Disease State

For some of the exploratory biomarker variables, an analysis will be performed to explore the relationship to disease state/progression. Disease state will be represented by CDR-SB score, and explorations may be carried out on the relationship between the biomarker variables and other measures of disease level. The biomarker variables will include, but not necessarily be limited to, plasma total tau concentration, plasma NFL concentration, and the vMRI measures for whole brain, hippocampus, temporal lobe and lateral ventricles. The relationship between change in CDR-SB score and change in biomarker will be explored.

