transformed variable. The model will include classification by time of observation, which can also be thought of as the visit at which the CDR-SB evaluation was done. The model will include classification by treatment and the interaction of treatment and time. The initial model will have interaction of the covariate with treatment, allowing the regression coefficient of the covariate to depend upon treatment. This interaction effect will be removed from the model if the statistic on the interaction is not significant at level 0.100 in the analysis with the final choice of the structure for the covariance matrix of the error term, as discussed in the paragraph that follows.

The initial model will impose no restrictions on the covariance matrix for the error term (using Option UN with the SAS REPEATED statement). A simpler structure for the covariance matrix will be considered, with the correlation coefficients for all pairs of times assumed to be the same while imposing no restrictions on the variances for the several times (using Option CSH with the SAS REPEATED statement). An approximate test of the hypothesis that the covariance matrix with the more complex model is same as the covariance matrix with the simpler model will be performed. The approximate test will be that based upon the difference in the values of $-2\log(\text{likelihood})$ for the two models, using the chi-square approximation for the null distribution, with degrees of freedom being the difference in the number of parameters required for the two structures of the covariance matrix. If the test statistic is not significant at level 0.050, the simpler model will be tentatively adopted. In that case, the compound symmetry structure (default option with the SAS REPEATED statement) will be considered. The approximate test for the comparison of the two models will again be performed. The compound symmetry model will be adopted only if the test statistic is not significant at level 0.050. If the computational algorithm does not satisfactorily converge with a particular structure assumed for the covariance matrix, that structure will not be adopted, and only the simpler structure(s) will be considered.

If the final model contains an effect for the interaction of treatment and covariate, the estimate for each of the four regression coefficients and for the average of the four regression coefficients will be provided. For each of the four regression coefficients

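### The tau PET model fixes equal residual variance at Weeks 44 and 96; if variance grows between visits, the Week 96 tests reject too often, and one extra parameter prevents it

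*SAP*

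**What the plan says.** SAP 13.0 (Analysis of Tau PET Scan Variables) fits Week 44 and Week 96 jointly for each brain region. It takes over the plasma NFL model and adds two assumptions. The first concerns the baseline term: "The baseline value will be a covariate, with the regression coefficient assumed to be the same for the two times of measurement". The second concerns the errors: "Compound symmetry will be assumed for the covariance matrix of the error terms of the two times of measurement". No reason is given, and there is no check of the structure, alternative structure or empirical standard error.

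The model being borrowed is less restrictive. For plasma variables, "an appropriate structure for the covariance matrix of the measurements of a subject will be selected". Dose effects are tested first as main effects across visits, and then: "These same tests will be provided for each time of measurement in the framework of the MMRM model". On which set leads, the SAP says that "the tests for the individual times will be given the greater attention if the statistic on the interaction of treatment and time" reaches the 0.100 level.

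Other models in the SAP treat the covariance differently. For the CDR-SB primary analysis (10.2), "An unstructured (co)variance structure will be used to model the within-patient errors". In the biomarker and CDR-SB relationship models of 13.0, the fit starts unstructured and is simplified stepwise: "The compound symmetry model will be adopted only if the test statistic is not significant at level 0.050". Protocol 8.1.5 names no covariance structure for tau PET.

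**The concern.** Compound symmetry has one variance and one covariance. With two visits there is only one correlation in any case, so the real restriction is that residual variance is the same at Week 44 and Week 96. In a progressive disease, subjects may spread apart as time from baseline increases. The model would then pool a smaller and a larger variance and apply the average to both visits, making the Week 96 standard error too small and the Week 44 one too large.

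The tests exposed are the Week 96 comparison of 2000 mg with placebo and the Week 96 dose-trend contrast. They are run for several regions and, under SAP 4.8.1, with four choices of reference region. If either is significant, the 1000 mg and 300 mg comparisons are formally considered. Week 96 is also the visit where a drug meant to slow tau accumulation would be expected to show its largest difference.

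**Working it through.** **Inputs from the documents.** Two visits with one common variance (SAP 13.0, tau PET). Two-sided level 0.050 (SAP 13.0, CSF tests, which the plasma and so the tau PET tests follow). Allocation 1:1:1:1 (SAP 4.2).

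**Inputs not in the documents.** Tau PET residual variances, between-visit correlation and number of subjects. SAP 14.0 says only that fewer subjects than anticipated will have tau PET data. Let k = Var(Week 96)/Var(Week 44), assumed to lie between 1 and 4. The plan states no precision or power figure for tau PET, so there is none to reproduce.

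**Step 1: per-visit tests, complete data.** Compound symmetry estimates the common variance as (V44 + V96)/2. Hence:

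- Week 96: model SE / true SE = sqrt((1 + k)/(2k))
- Week 44: model SE / true SE = sqrt((1 + k)/2)
- actual two-sided error = 2 × Phi(−1.96 × ratio)

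For k = 2 at Week 96: sqrt(3/4) = 0.866, 1.96 × 0.866 = 1.697, error 9.0%. At Week 44: sqrt(3/2) = 1.225, 1.96 × 1.225 = 2.401, error 1.6%.

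| k | Week 96 SE ratio | Week 96 error | Week 44 SE ratio | Week 44 error |
|---|---|---|---|---|
| 1.0 | 1.000 | 5.0% | 1.000 | 5.0% |
| 1.25 | 0.949 | 6.3% | 1.061 | 3.8% |
| 1.5 | 0.913 | 7.4% | 1.118 | 2.8% |
| 2.0 | 0.866 | 9.0% | 1.225 | 1.6% |
| 4.0 | 0.791 | 12.1% | 1.581 | 0.2% |

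**Step 2: main effect across visits, complete data.** With covariance C, the true variance of a subject's two-visit mean is (V44 + V96 + 2C)/4. Under compound symmetry the model uses (2 × (V44 + V96)/2 + 2C)/4, which is the same. The two errors cancel and the test is sound.

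**Step 3: simulation with no treatment effect.** Four arms, REML, Satterthwaite degrees of freedom, one common baseline slope, 1,500 to 2,000 runs per scenario (Monte Carlo error about 0.5 to 0.9 percentage points). Rejection rate for 2000 mg against placebo at Week 96, with 25 per arm and correlation 0.6:

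| k | Compound symmetry, complete | Unstructured, complete | Compound symmetry, 30% missing at Week 96 | Unstructured, 30% missing |
|---|---|---|---|---|
| 1.0 | 4.2% | 4.2% | not run | not run |
| 1.5 | 7.8% | 5.8% | 6.9% | 4.3% |
| 2.0 | 8.4% | 4.1% | 9.6% | 5.2% |
| 4.0 | 12.3% | 4.9% | 15.4% | 5.9% |

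Missing data were completely at random. With k = 2 and 30% missing, compound symmetry gave 9.5% with 15 per arm, 11.6% at correlation 0.3 and 11.2% at correlation 0.85. The unstructured model gave 5.6%, 6.0% and 4.7%. The trend contrast at Week 96 behaved alike under compound symmetry (6.8% to 15.3% for k above 1).

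The main-effect test under compound symmetry rejected 4.3% to 5.3% of the time with complete data. With 30% missing at Week 96 the range was 5.4% to 8.4%, lowest at k = 1.5 and highest at k = 4. The lower end is within simulation error of 5%. The cancellation in Step 2 needs both scans from each subject.

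**The case against.** The strongest reply is that little depends on this model. Tau PET is an exploratory objective in a subset of subjects. It lies outside the hypotheses in SAP 10.7 and drives no stated interim decision. The SAP is open about adding assumptions, and expects few scans. It also puts the main effect first unless treatment-by-time is significant at 0.100, and with complete data that test is sound. All of this stands and limits the importance of the point. The small sample does not justify the restriction, however: the unstructured model stayed between 4.1% and 6.0% at Week 96 even with 15 per arm and 30% missing.

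A second reply is that the variance ratio is unknown. That also stands: at k = 1 there is no error, and at 1.25 it is small. If variance fell over time, Week 44 would be the visit with too many rejections.

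A third is that the CDR-SB models are not close comparators, since they have three or four visits and tau PET was taken out of the relationship analyses. This is fair, but the plasma model that tau PET borrows from also leaves the structure to be selected.

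A reader might infer more than the documents support:

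- **Cascade into component regions.** SAP 4.8.1 opens the individual regions when a composite gives evidence of an effect. It does not tie that evidence to Week 96, so the main effect could equally be the trigger.
- **The common baseline slope.** No harm from it has been shown. With randomised arms it mainly affects precision. The plasma NFL model does not keep a visit-specific slope regardless; it removes that term unless significant at 0.100.
- **The one-year gap.** It does no harm in itself; it is only a reason why the variances may differ.

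The skewness-based transformation rule in 13.0 is not a planned remedy, because unequal variance does not trigger it.

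**Conclusion.** The point holds as a conditional one. If tau PET residual variance is larger at Week 96 than at Week 44, the prescribed model understates the Week 96 standard error. For variance ratios of 1.25 to 2.0 the nominal 5% test then has a true error of about 6% to 9%, and Week 44 loses power. These figures are for complete data and an assumed ratio; confidence is high in the mechanism, not in its size in this trial.

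The main-effect test is essentially valid with complete data, but drifts upward when Week 96 scans are missing and the variance growth is marked. It would go too far to conclude that tau PET findings will be false, or that the trial's primary result is at risk: the variances are not given, the main effect normally leads, and tau PET is outside the family-wise error control. This is a cheap improvement.

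**What to change.** In SAP 13.0 (Analysis of Tau PET Scan Variables), replace the compound symmetry sentence with one specifying an unstructured 2x2 covariance matrix for Weeks 44 and 96. It needs three covariance parameters instead of two, and nothing else in the model has to change.

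Heterogeneous compound symmetry should not be listed as a fallback: with two visits it has two variances and one correlation, and so is the same model.

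If the sponsor wishes, the plasma rule for the baseline-by-time term (keep it only if significant at 0.100) could be applied here too. That would be a second edit for consistency, and the error described above does not depend on it.

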The schedule of visits for which the biomarker measurements are obtained are not the same as the schedule of visits on which the CDR-SB assessments are done. For plasma concentration variables and vMRI variables, respectively, the visits defining the bivariate observations composing the data sets on which the analyses will be performed are shown in the two tables that follow. Although there were times of evaluation before Week 48 for both plasma concentration biomarkers and CDR-SB, there was no pair of visits before Week 48 for which the blood sample for the biomarkers and the CDR-SB evaluation were judged to be close enough in time to form an acceptable bivariate observation.

Bivariate Observations for CDR-SB and Plasma Concentration Variable		
Observation	Visit for CDR-SB Score	Visit for Plasma Concentration
1	Week 48	Week 48
2	Week 72	Week 72
3	Week 96	Week 96

Bivariate Observations for CDR-SB and vMRI		
Observation	Visit for CDR-SB Score	Visit for vMRI Measurement
1	Week 24	Week 28
2	Week 48	Week 44
3	Week 72	Week 68
4	Week 96	Week 96

For each biomarker variable, the bivariate data of CDR-SB and the biomarker variable for each combination of treatment and time of observation will be plotted. With each plot Spearman's rank correlation coefficient and the p-value for the test of independence will be provided. An investigation of the relationship of CDR-SB with the biomarker variable for all of the times of observation jointly will be carried out in the framework of a MMRM analysis with decrease from baseline in CDR-SB score as the response variable and with change from baseline in the biomarker variable as a covariate (explanatory variable) that changes with time. If a transformation is used for the analysis of the biomarker variable itself, that same transformation will be used for the biomarker variable in this analysis; that is, the covariate will be the change from baseline in the value of the

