and for their average, a two-tailed test of the hypothesis that the regression coefficient (or the average) = 0 will be performed at significance level 0.050. This will serve as a test of the hypothesis that the correlation coefficient between the CDR-SB change from baseline and the biomarker change from baseline is 0. If the final model does not contain an effect for the interaction of treatment and covariate (a common regression coefficient for all four treatments), this hypothesis test will be performed on the single regression coefficient and will apply to placebo and all three ABBV-8E12 treatments.

To give further confidence in the assessment of the relationship of the biomarker variables with disease state and progression in the absence of treatment with ABBV-8E12, a MMRM analysis will be performed on the data set restricted to subjects on the placebo treatment. The model and analysis will be simpler than that described above in that there will be no effects involving treatment. In particular, there will be only a single regression coefficient.

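### The biomarker–CDR-SB change model has no baseline terms, so a rejection does not show a link with progression beyond shared dependence on baseline severity; a baseline-adjusted coefficient should stand beside it

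*SAP*

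**What the plan says.** SAP 13.0, under Relationship with Disease State, specifies the joint analysis for each biomarker as an "MMRM analysis with decrease from baseline in CDR-SB score as the response variable and with change from baseline in the biomarker variable as a covariate", the covariate varying with time. The remaining terms are named one by one: "The model will include classification by time of observation"; "The model will include classification by treatment and the interaction of treatment and time"; and "The initial model will have interaction of the covariate with treatment", the last to be removed if not significant at 0.100. The text goes on to the order in which covariance structures are tried, but names no baseline covariate.

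A second fit uses placebo subjects only: "The model and analysis will be simpler than that described above in that there will be no effects involving treatment". Nothing is added to it.

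Inference is a "two-tailed test of the hypothesis that the regression coefficient (or the average) = 0 will be performed at significance level 0.050". The SAP states what this tests: "This will serve as a test of the hypothesis that the correlation coefficient between the CDR-SB change from baseline and the biomarker change" is zero. Spearman correlations are also planned, separately for each treatment and time, again without adjustment.

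The same variables are baseline-adjusted elsewhere. SAP 10.2 puts baseline CDR-SB and its interaction with visit into the primary MMRM. SAP 13.0 puts the baseline value into the plasma tau and NFL models, initially by time, and into the vMRI model together with an "additional covariate, estimated total intracranial volume (eTIV), in the model". Protocol 8.1.5 announces the exploration without naming covariates.

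**The concern.** The stated purpose is to learn how the biomarkers relate to disease state and progression, and the placebo-only fit is offered as further support. Suppose that how impaired a subject is at entry predicts both later CDR-SB change and later biomarker change. The two changes are then correlated even if, among subjects with the same starting point, one says nothing about the other. The planned coefficient would be non-zero for that reason alone.

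The other planned outputs cannot tell the two explanations apart. Restricting to placebo removes treatment effects but leaves baseline severity in place, and the Spearman coefficients are unadjusted too. What is at stake is the interpretation of an exploratory result: whether NFL, tau or a brain volume tracks progression, or only reflects where subjects started.

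**Working it through.** The documents give no power or error figure for this analysis, so there is none to reproduce.

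**Inputs**
- Test level 0.05, two-tailed (SAP 13.0).
- 400 subjects, 100 per group; 25% assumed without post-baseline data (SAP 4.3). That leaves 400 × 0.75 = 300 and 100 × 0.75 = 75.
- Paired observations: four for vMRI, three for plasma (tables in SAP 13.0).
- r, the correlation of baseline severity with each change: not in the documents, so varied from 0 to 0.5.

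**Step 1: terms side by side**

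| Model | Baseline CDR-SB | Baseline biomarker | eTIV |
|---|---|---|---|
| Primary CDR-SB MMRM (SAP 10.2) | yes, by visit | not applicable | not applicable |
| Plasma MMRM (SAP 13.0) | no | yes, initially by time | not applicable |
| vMRI MMRM (SAP 13.0) | no | yes, initially by time | yes |
| Relationship MMRM, all subjects (SAP 13.0) | no | no | no |
| Relationship MMRM, placebo only (SAP 13.0) | no | no | no |

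**Step 2: the mechanism at a single visit**

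If each change correlates r with baseline severity and the changes are otherwise unrelated, their unadjusted correlation is ρ = r × r. With m = atanh(ρ) × √(n − 3), the chance of rejecting zero correlation is Φ(m − 1.96) + Φ(−m − 1.96). For n = 400 and r = 0.3: ρ = 0.09, m = 0.0902 × 19.92 = 1.80, and the rate is Φ(−0.16) + Φ(−3.76) = 43.6%.

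| n | r = 0 | r = 0.2 | r = 0.3 | r = 0.5 |
|---|---|---|---|---|
| 75 | 5.0% | 6.3% | 11.9% | 58.2% |
| 100 | 5.0% | 6.8% | 14.4% | 71.1% |
| 300 | 5.0% | 10.6% | 34.3% | 99.3% |
| 400 | 5.0% | 12.5% | 43.6% | 99.9% |

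This shows direction only. The planned model is a repeated-measures one.

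**Step 3: repeated-measures simulation**

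Four visits (Weeks 24, 48, 72, 96), complete data, unstructured covariance, a common slope for the biomarker covariate, critical value 1.96. Each subject's underlying slope on each measure has correlation r with a standardised baseline severity; the two slopes share nothing else. Visit values are slope × (week/96) plus noise of SD 0.3. Baseline CDR-SB is taken to equal severity, and baseline biomarker to correlate 0.5 with it. Each data set was fitted with the terms the SAP lists, then with both baselines by visit added.

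| Setting | r | As listed | Both baselines added |
|---|---|---|---|
| Placebo only, n = 100 (1000 runs) | 0 | 4.9% | 4.7% |
| | 0.2 | 6.6% | 7.0% |
| | 0.3 | 7.7% | 7.0% |
| | 0.5 | 23.7% | 6.2% |
| All subjects, n = 400 (500 runs) | 0 | 3.8% | 3.8% |
| | 0.2 | 7.0% | 3.8% |
| | 0.3 | 13.6% | 6.2% |
| | 0.5 | 71.2% | 4.4% |

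The simulation standard error near 5% is √(0.05 × 0.95/1000) = 0.7 points at n = 100 and √(0.05 × 0.95/500) = 1.0 point at n = 400. The adjusted 7.0% at n = 100 is probably slight small-sample inflation.

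**The case against.** The strongest reply is that the SAP asks an unadjusted question and answers it correctly. Its null is zero correlation between two changes. If both depend on starting severity, that correlation really is non-zero and rejecting is right. This stands. A reader might infer that the planned test has an inflated type I error; for the null as written it does not. The percentages above measure how often a rejection would mislead someone who reads it as a link beyond baseline severity.

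The contrast with the treatment-effect models is likewise not a contradiction. Those models compare randomised arms; this one relates two change scores, and each baseline is part of its own change score, so conditioning on it alters the meaning of the slope. That supports reporting both coefficients rather than replacing one.

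Four stronger readings are tempting but unsupported:
- That the single-visit rates apply. At n = 400 and r = 0.3 they give 43.6%, against 13.6% in the repeated-measures simulation, which is closer to the plan.
- That subjects who are more impaired at entry are known to decline faster on both measures. The documents do not say so, and entry at CDR global 0.5 with MMSE 22–30 narrows the severity range and may lower r.
- That the result feeds Phase 3 decisions. The SAP ties acceleration of Phase 3 to criteria at the interim efficacy analyses (4.4), and the target-engagement analysis only guides whether an early futility analysis is run. Neither uses this model.
- That leaving out eTIV creates the severity problem. eTIV reflects head size, so its omission bears on the scaling and noise of absolute volumes.

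**Conclusion.** The point holds as one of interpretation. As planned, a significant coefficient supports the statement that the two changes are correlated. It does not support a relationship with progression over and above where subjects started, and neither the Spearman correlations nor the placebo-only fit closes that gap.

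The size rests on r, which is assumed. In the all-subject analysis the effect is small at r = 0.2, moderate at 0.3 and large at 0.5. In placebo alone it is slight up to 0.3, where adjustment makes little difference, and material only at 0.5. Three features of the simulation limit it. It uses four visits, which fits vMRI but not the three plasma pairs. It has no missing data. It also treats baseline CDR-SB as an error-free measure of severity, so the return to about 4–6% at n = 400 is a best case; in practice adjustment would reduce the confounding and may not remove it.

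The analysis is exploratory and lies outside the family-wise error control in SAP 10.7, so no efficacy, safety or stopping conclusion is affected. This is an inexpensive improvement, not an error in the plan.

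**What to change.** Keep the planned unadjusted coefficient and its zero-correlation test. Beside it, in both the all-subject and the placebo-only models, report a coefficient adjusted for baseline CDR-SB and the baseline biomarker value, each by time, with the baseline biomarker on the same transformed scale as the change. Base any statement about a relationship with progression on the adjusted coefficient. For vMRI, also include eTIV, for consistency with the vMRI treatment-effect model and for head-size scaling, not as a severity adjustment.

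The cost is about one sentence in SAP 13.0 and one further fit per biomarker and model. All the covariates are already planned for other models, so no new data are needed.

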4.3 Sample Size

Approximately 400 Early AD subjects (100 subjects/group) will be enrolled and randomized into three ABBV-8E12 dose groups and placebo with 1:1:1:1 randomization ratio. This sample size has about 80% power to detect an ABBV-8E12 treatment effect size (vs. placebo) of 0.45 for both the high dose and the middle dose and 0.28 for the low dose on CDR-SB score changes from baseline up to Week 96 using one-sided test at the 2.5% significance level with Bonferroni method to adjust multiplicity. This power assessment was based on the assumption that 25% subjects do not have post-baseline data and the calculation was conducted using Cytel EAST version 6.4.

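### SAP 13.0 drops a non-significant biomarker-by-treatment interaction and then applies one CDR-SB slope test to all four arms, which does not show that the relationship holds in each arm

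*SAP*

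**What the plan says.** In SAP 13.0, under Relationship with Disease State, the joint model has decrease from baseline in CDR-SB as the response and change from baseline in the biomarker as a time-varying covariate. It starts with a separate biomarker slope in each arm. Then: "This interaction effect will be removed from the model if the statistic on the interaction is not significant at level 0.100".

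The output depends on that result.

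- **Interaction kept:** "the estimate for each of the four regression coefficients and for the average of the four regression coefficients will be provided". For each of these, "a two-tailed test of the hypothesis that the regression coefficient (or the average) = 0 will be performed at significance level 0.050".
- **Interaction dropped:** there is one slope, and "this hypothesis test will be performed on the single regression coefficient and will apply to placebo and all three ABBV-8E12 treatments".

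Two analyses run in either case. Each treatment-by-visit plot comes with a rank correlation: "Spearman's rank correlation coefficient and the p-value for the test of independence will be provided". For the relationship without active treatment, "a MMRM analysis will be performed on the data set restricted to subjects on the placebo treatment".

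The section sets no margin for treating slopes as equal. It promises estimates and tests of the slopes but mentions no confidence intervals. Neither document states an expected biomarker–CDR-SB correlation or the power of the interaction test.

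**The concern.** Failing to reject equality of four slopes is not evidence that they are equal. A pooled slope is a legitimate summary. Saying that its test applies to each arm goes further, because a slope carried by three arms can make the pooled test significant and the result is then attributed to a fourth arm where the link may be absent.

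This matters for interpretation. Whether treatment alters the link between a biomarker and decline bears on whether the biomarker can be read as a marker of response in treated subjects. When the interaction is dropped, the reader gets no model-based slope for any ABBV-8E12 arm from which to judge this.

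**Working it through.** **1. Sample size, and the plan's own figure.** SAP 4.3 states "Approximately 400 Early AD subjects (100 subjects/group) will be enrolled", "with 1:1:1:1 randomization ratio", and assumes 25% without post-baseline data, so 100 × 0.75 = 75 per arm. Its power statement uses effect sizes 0.45, 0.45 and 0.28 and one-sided 2.5% with Bonferroni (0.025/3 = 0.00833 per dose).

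- One dose at 0.45: Φ(0.45 × √(75/2) − 2.394) = Φ(2.756 − 2.394) = 64%.
- At least one of three doses, sharing one placebo arm (simulated): 80.7%, against the stated figure of about 80%.

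The stated power is reproduced, which supports 75 per arm as the working number. It concerns the primary endpoint and says nothing about the interaction test.

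**2. Single-visit benchmark.** Assume correlation r in three arms, zero slope in the fourth, and equal variances. With slopes β, β, β, 0 the mean is 0.75β, and the sum of squared deviations is 3(0.25β)² + (0.75β)² = 0.75β². The noncentrality of the 3-df test is therefore λ = n × 0.75 × r²/(1 − r²). Power at level 0.10 comes from the noncentral F.

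| n per arm | r | λ | Power | Missed |
|---|---|---|---|---|
| 75 | 0.2 | 2.34 | 33% | 67% |
| 75 | 0.3 | 5.56 | 61% | 39% |
| 75 | 0.4 | 10.71 | 87% | 13% |
| 100 | 0.2 | 3.13 | 40% | 60% |
| 100 | 0.3 | 7.42 | 73% | 27% |

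Power falls below 50% only if r is under about 0.26 (n = 75) or 0.23 (n = 100). In simulation at n = 75, the interaction is missed and the common slope is also significant in 51%, 41% and 15% of trials at r = 0.2, 0.3 and 0.4.

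**3. Repeated visits, idealised.** SAP 13.0 pairs CDR-SB with plasma at three visits (Weeks 48, 72, 96) and with vMRI at four. With known compound-symmetry covariance, λ is multiplied by (1+(T−1)rx)/(1+(T−1)re) + (T−1)(1−rx)/(1−re). Here rx and re are the within-subject correlations of biomarker and error, assumed to be 0.6–0.9 and 0.6–0.8. At n = 75 with three visits, power is 49–89% at r = 0.2 and 84–99.8% at r = 0.3. This treats the biomarker as measured without error, so it is optimistic.

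**4. Repeated visits with measurement noise.** Simulated trials, 75 per arm. Assumptions: slope correlation 0.5 in three arms and 0 in the 2000 mg arm; CDR-SB slope SD 2 and visit noise 0.8; biomarker noise as a fraction of its slope SD; unstructured covariance. The interaction is tested at 0.10. If it is dropped, the common slope is tested at 0.05. The wrong-assertion column is missed × significant-if-missed.

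| Data | Biomarker noise | Missed | Common slope significant, if missed | Wrong assertion | Missed, no baseline noise |
|---|---|---|---|---|---|
| Plasma | 0.2 | 27% | 99% | 27% | 18% |
| Plasma | 0.4 | 55% | 82% | 45% | 44% |
| Plasma | 0.7 | 77% | 46% | 35% | 69% |
| vMRI | 0.2 | 32% | 99% | 32% | 21% |
| vMRI | 0.4 | 65% | 77% | 50% | 56% |
| vMRI | 0.7 | 80% | 38% | 30% | 77% |

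Across repeated runs, with and without baseline noise, misses span about 16–81% and wrong assertions about 16–52%. With no link in any arm, the tests hold roughly their nominal size (interaction 0.10–0.11, common slope 0.045–0.065).

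**5. Why steps 3 and 4 differ.** In step 4 the covariate is a noisy change from baseline. The model gives weight to within-subject fluctuation that is largely noise, so extra visits help little. At the highest noise level, with baseline noise, the Week 96 correlation in the linked arms is about 0.31. The noisy model misses 77–80% there. Near r = 0.3, the single-visit test misses 39% and the idealised repeated-visit model at most 16%.

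**The case against.** A reader might infer that the interaction test usually misses a relationship absent in one arm. The documents do not support that. They give no correlation or biomarker noise, and under low noise or r of 0.3 and above at a single visit, the test finds the discrepant arm more often than not. The harmful outcome also needs a significant common slope, and in these cases it never clearly exceeds half of trials. Every scenario assumes a link of exactly zero in one arm; partial weakening was not examined.

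A reader might also take the SAP to claim proven equality. It does not say so. The sentence can be read as giving the scope of the reduced model's test, and an equivalence margin belongs to a claim the SAP never makes. Removing non-significant terms at 0.100 is also its convention elsewhere in Section 13.0.

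The strongest point is that much is already planned. The Spearman output gives 4 × 3 = 12 arm-by-visit correlations per plasma biomarker and 4 × 4 = 16 per vMRI measure. In simulated trials where the common slope would be wrongly attributed to 2000 mg, the Week 96 Spearman test for that arm was non-significant in 91–95%. The placebo-only model covers the case where placebo is the discrepant arm.

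These points stand and limit the concern. They do not remove it. A non-significant Spearman p-value beside a pooled result said to apply to that arm leaves the conflict unresolved, and no model-based slope or interval is promised for an active arm.

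**Conclusion.** The concern holds in a limited form. The rule lets a non-significant 3-df test lead to one slope test being applied to every arm, which that test cannot justify. Under the assumed values, a zero slope in one arm is missed in about 16–81% of trials and the link is wrongly attributed to that arm in about 16–52%. These figures rest on 75 per arm, slope correlation 0.5 against 0, and noise levels chosen for illustration. The width of the ranges reflects what the documents leave unspecified.

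It would be wrong to infer any threat to the main result. The biomarker–CDR-SB analysis is exploratory, and no alpha allocation, stopping rule, or primary or key secondary conclusion depends on it. This is a worthwhile reporting improvement.

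**What to change.** In SAP 13.0, report the four arm-specific coefficients with 95% confidence intervals from the interaction model, under the finally chosen covariance structure, whatever the interaction p-value. Present the common coefficient as an average over arms. Replace the statement that the single test "this hypothesis test will be performed on the single regression coefficient and will apply to placebo and all three ABBV-8E12 treatments" with one saying that the common coefficient summarises the four arms and does not show that the relationship holds in each.

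The cost is one changed sentence and one extra table per biomarker from a model already fitted. The downside is wide intervals. For a single-visit correlation of 0.3 with n = 75, Fisher's z gives 0.310 ± 1.96/√72, or about 0.08 to 0.49. That width tells the reader how much the data can say about any one arm.
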